- (c) Core biopsy should definitively demonstrate invasive carcinoma.
- (d) Invasive carcinoma should be ER α receptor positive
- (e) The tumor should be approximately at least 1 cm, to account for variability in imaging and imaging occult disease (physical exam, mammography, ultrasound). We recognize that from time to time because of this variation, there might

not be enough tissue available for analysis after surgical excision but this will allow the greatest opportunity to capture as many eligible patients as possible.

- (f) Patients in whom surgical excision of the tumor is part of standard of care management
- (g) ECOG score of 0 or 1
- (h) Negative serum or urine β -hCG pregnancy test at screening for patients of child-bearing potential (this is routinely done if the patient is premenopausal and having surgery)
- (i) Consent to participate in DBBR (RPCI only)

Exclusion Criteria:

- (a) Male patients are not eligible for this study
- (b) Female patients with inoperable tumors or women with stage 4 disease diagnosed on CT, PET, PET/CT or bone scan.
- (c) Patients with diagnosis by FNA cytology only
- (d) Pregnant or lactating women
- (e) Prior therapy for breast cancer, including irradiation, chemo- immuno- and/or hormonal therapy
- (f) Patients receiving any hormonal therapy, e.g. ovarian hormonal replacement therapy, infertility medications etc., are not eligible
- (g) Nonmalignant systemic disease (cardiovascular, renal, hepatic, etc.) that would preclude the patient from being subjected to surgical excision
- (h) Psychiatric or addictive disorders that would preclude obtaining informed consent
- (i) Patients known or suspected to have hypercoagulable syndrome or with history of venous or arterial thrombosis, stroke, TIA, or pulmonary embolism
- (j) Women with non-invasive disease or microinvasion are not eligible.
- (k) Women undergoing neoadjuvant chemotherapy are not eligible
- (l) women currently on tamoxifen and raloxifene for prevention are not eligible
- (m) Patients shall not receive any herbal/alternative therapies such as flaxseed or soy products or black cohosh.
- (n) Patients with a known mutation in p53 (Li Fraumeni Syndrome)

Unevaluable patients are defined as patients who do not have enough tissue for study or who come off early on tamoxifen, and will be replaced on study.

IV. TREATMENT PLAN AND RESEARCH METHODS:

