A PK structural model will be developed for tamoxifen, and potentially including its various metabolites. The physiologic pharmacokinetic models explored will be described by the estimation of mean structural model parameters (e.g., plasma volumes of distribution and clearances), the magnitude of inter-individual variability (IIV) in these parameters, and the magnitude of residual variability (RV). It is anticipated that the appropriate PK model will initially include either a one- or two-compartment model with first-order absorption and (linear) elimination. The PK model could expand to include mechanistic attributes, such as a receptor-mediated clearance mechanisms (58, 59) since tamoxifen binds to the estrogen receptor and may in part, get internalized as a complex, undergoing receptor-mediated

predict pharmacokinetic outcomes of various exposure regimens. (58) (59).

Lumpectomy or Mastectomy Specimens:

Surgical specimen upon resection will be transported in ice from the operating room to mammography if the specimen is a needle localization and then to pathology on ice. Mastectomy specimens and lumpectomy specimens will be transported to pathology via a research assistant, the tube system or via HCA to pathology. The specimen should be received by pathology within 30 minutes. Specimens will be processed by institutional pathologist as per standards of care which include immediate gross examination. A sample of grossly identified tumor tissue will be frozen to -70°C . The benign core biopsy samples will also be snap frozen. The frozen tissue from the University of Chicago will be sent via fed-ex (overnight) on dry ice the same day to laboratory of [name] at Roswell Park Cancer Institute. Tissue shipments should be to the attention of [name] at Roswell Park Cancer Institute. Shipping address: [name], [name], Roswell Park Cancer Institute, [name]. Please also e-mail [contact]. If the surgical sample is harvested on Friday, it will be stored at -70 over the weekend and shipped on Monday morning. At RPCI, the frozen tissue will be submitted to laboratory of [name] (PI). Further IHC studies of p53 and ER targets will be conducted in the core biopsy samples and surgically excised tumor tissue of the study subjects using a tissue microarray.

Expression analysis of selected ER and p53-target genes:

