Expression of selected p53 and ER-target genes will be analyzed. All IHC staining will be performed utilizing the AutoStainer™ series of automated stainers (Dako-Cytomation, California) retrospectively in the pre-surgical tumor biopsies and in the resected tumors from the breast cancer surgery. The percentage of tumors that are positive for ER α will be recorded, and a tumor will be considered positive if the Allred score is greater than 3. Staining for p21, Bax, puma and Survivin will be evaluated qualitatively and scored on a 0 – 3+ intensity scale (0 = negative staining, 1+ = weak staining, 2+ = moderately intense staining, and 3 + = strong staining). Antibodies against ER α , p53, and Survivin have already been optimized.

Analysis of ER α -p53 interaction in patient tumor tissues:

ChIP and quantitative ChIP (ChIP followed by quantitative RT PCR) assays and proximity ligation assay (PLA) are regularly used in our laboratory to analyze ER α -p53 interaction in cultured breast cancer cells. We have adapted a method others have previously reported for ChIP assay in tissues (60) to analyze tumor tissue in human breast cancer xenograft in mice and was successful in analyzing ER α -p53 interaction. We will use this protocol to analyze ER α -p53 interaction in human breast cancer tissues.

At RPCI, the frozen tissue from surgically excised tumor will be submitted to the laboratory of [name]. Further IHC studies of p53 and ER targets will be conducted in the core biopsy samples (unstained slides will be requested for biopsies performed outside RPCI) and surgically excised tumor tissue of the study subjects. Tissue microarray (TMA) will be generated from surgically excised tissue and IHC and PLA will be performed on these TMAs.

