We have been successful with ChIP assays in both fresh and recently frozen mouse tissues. If a patient consents to fresh tissue collection and the tissue procurement resource contains insufficient sample to release for testing, this testing will not be required. The frozen tissue from the University of Chicago will be sent via FedEx on dry ice the same day to the laboratory of [name] at Roswell Park Cancer Institute [name]. If the surgical sample is harvested on Friday, it will be stored at -70 over the weekend and shipped on Monday morning. In addition, PLA for protein-protein interaction will be performed in [name] laboratory on unstained slides of tumor specimens provided by [name] (Department of Pathology, RPCI). Similarly, PLA will be performed on unstained slides of tumor specimens sent (by FedEx, overnight) from University of Chicago to the laboratory of [name] at RPCI.

Determination of p53 sequence in tumor samples:

All evaluations will be done blindly in the absence of any identifying information from IHC as to the intensity of p53 staining. Various studies have indicated that IHC by itself may not be a reliable method to determine p53 status in tumors. As explained above, IHC determination is based on the assumption that mutant p53 is more stable leading to higher signal in IHC. However, that is not always the case. For example, 20% of tumors with a mutant p53 did not show nuclear accumulation of the protein (2). Sequence determination of p53 gene is more precise in determining wild

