First, we will analyze if ER α -p53 interaction in tumors affects p53's function as a transcriptional regulator. Toward this goal, we will analyze a selected group of p53-target genes (based on their reported importance in regulating cell cycle and apoptosis (63,64) that are either activated or repressed by p53 in the resected tumor tissue. . ***We have already demonstrated that Survivin (whose transcription is known to be repressed by p53) expression is upregulated as a consequence of ER binding to p53, and treatment with TAM leads to functional activation of p53, thereby restoring p53's ability to repress Survivin expression (65).*** The mRNA levels of these genes will be analyzed by qRT-PCR, a technique routinely used in the PI's laboratory. Subsequently, we will analyze the expression of these genes at the protein level. Immunohistochemistry (IHC) studies of these proteins will be conducted in the core biopsy samples (unstained slides will be requested for biopsies performed outside RPCI) and surgically excised tumor tissue of the study subjects using a tissue microarray (TMA) generated by the Department of Pathology under the supervision of [name]. For patients recruited at the University of Chicago, TMA will be generated at the University of Chicago. IHC will be performed under the direction of the pathologist, with all pathology personnel blinded to treatment assignment. The IHC endpoints will be rounded to the nearest 10% by the pathologist who will be blinded to the treatment group assignment. The ER and p53 status will be determined as described in the earlier section (section 4.1.1). Staining for p21, Bax, puma and Survivin will be evaluated qualitatively and scored on a 0 – 3+ intensity scale (0 = negative staining, 1+ = weak staining, 2+ = moderately intense staining, and 3 + = strong staining. It is to be noted that p53-target gene protein expression will be analyzed by IHC both in the core biopsy samples and surgically excised tumor tissue enabling within-patient comparison of expression profile of these proteins *before* and *after* TAM therapy. Ideally, a similar within-patient approach is desirable for other assays (ChIP and qRT-PCR,) as well. However, it is practically impossible given the limited tissue availability from the pre-surgical biopsy.

VI. STATISTICAL CONSIDERATIONS

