The bio-statistician at RPCI will perform the statistical analyses and aid in interpretation of results. Exploratory graphical analysis and data confirmation will precede formal inferential analysis. As this is an investigational study, no correction for multiple testing will be made; p-values less than $\alpha=0.05$ will be deemed statistically significant. While formal power computations are provided, it is expected a larger Phase III trial will be planned to confirm and elaborate promising findings. The demographic and baseline data will be summarized by treatment group. Descriptive statistics such as frequencies and relative frequencies will be computed for all categorical variables. Numeric variables will be summarized using simple descriptive statistics such as mean, standard deviation, quartiles, etc. Ninety-five percent confidence intervals will be computed when appropriate. A variety of graphical techniques will be used to display data.

The primary analyses in Aim 1 are comparisons of ER α -p53 interaction (positive or negative) between independent treatment and control groups. The proportions of patients with positive ChIP assay/PLA will be compared with Fisher's Exact Test, which has 80% power to detect a difference of about 0.41 between the two group; e.g., a difference of 70% in the control group vs. 30% in the TAM group. In Aim 2, mean mRNA levels, as measured by qRT-PCR, will be compared across treatment and control groups. The difference in log fold intensity between treatment and control will be estimated with an independent samples t-confidence interval. The corresponding hypothesis test has

80% power to detect an effect size of 0.91. That is, if the true difference in means is about 0.91 standard deviations, there is an 80% probability our study will correctly reject the null hypothesis of no effect.

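### The Aim 1 positive/negative ChIP/PLA call has no written masking to arm and no fixed rule for combining the two assays: an unprotected route to bias, cheap to close

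*Combined protocol and SAP*

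**What the plan says.** **Endpoint.** Section VI makes the Aim 1 primary analysis a between-arm comparison of a positive-or-negative ERα-p53 interaction: "The proportions of patients with positive ChIP assay/PLA will be compared with" Fisher's exact test. It claims 80% power for a difference of about 0.41, gives 70% (control) against 30% (tamoxifen) as the example, and makes no correction for multiple testing.

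**Where the call is made.** Section IV gives arm 1 no intervention, and no placebo is described. Section V (Lumpectomy or Mastectomy Specimens) says of RPCI tumor that "the frozen tissue will be submitted to laboratory of [name] (PI)". Section V (Analysis of ERα-p53 interaction) says that "ChIP and quantitative ChIP (ChIP followed by quantitative RT PCR) assays and proximity ligation assay (PLA) are regularly used in our laboratory", and that "PLA for protein-protein interaction will be performed in [name] laboratory on unstained slides of tumor specimens provided by" Pathology.

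**What is masked.** Section V (Analysis of p53-target gene transcription) states: "IHC will be performed under the direction of the pathologist, with all pathology personnel blinded to treatment assignment". The p53 sequencing section states: "All evaluations will be done blindly in the absence of any identifying information from IHC as to the intensity of p53 staining".

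**Missing tissue.** Section V says that if "the tissue procurement resource contains insufficient sample to release for testing, this testing will not be required". The eligibility section says: "Unevaluable patients are defined as patients who do not have enough tissue for study or who come off early on tamoxifen", and has such patients replaced.

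**The concern.** The primary endpoint is a laboratory judgement with a predicted direction: more positives in control than on tamoxifen. The plan protects its IHC readings with masked pathology staff and, for the p53-target proteins, a written 0 to 3+ scale. It writes neither protection for ChIP or PLA, which decide Aim 1. If arm is known when calls are made, or the way of combining the assays is settled after arm is known, a false positive becomes more likely. Section II says a positive finding would lead straight to a large randomized trial, so the result will be used.

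**Working it through.** **1. Does any masking sentence reach ChIP or PLA?**
- The section V sentence on masking to arm names IHC and pathology personnel only.
- The sequencing sentences that use the word blindly mean blind to p53 IHC staining intensity, not to arm.
- Pathology supplies the RPCI slides for PLA, and PLA shares tissue microarrays with IHC. Masking the supplier does not mask a reader in another laboratory.
- ChIP uses frozen tumor sent to the PI's laboratory.

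So no masking to arm is stated for either assay in the supplied text.

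**2. Could arm reach the laboratory?** Section IX makes each site PI responsible for close monitoring of subjects and has the PI or a designee complete the serious adverse event forms. Appendix 2, item 6, makes the PI responsible for drug accountability, recorded by patient ID, though this can be delegated. Only arm 2 takes the drug, so a patient's entry in that record reveals arm. Arm information can therefore reach the head of the laboratory that receives the tumor. Nothing says that it reaches the bench.

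**3. Is the readout fixed?** Section VI writes ChIP and PLA with a slash and no rule for one, either or both. The Background reports preliminary ChIP in patient tumors with IgG and non-specific-site negative controls on two promoters (p21 and survivin), but sets no rule for the trial. No negative control is described for PLA. The plan does not say whether a patient with only one assay result has enough tissue to be evaluable.

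**4. The plan's own power.** Inputs: 50 patients (section IV, Enrollment), taken as 25 per arm since blocks of four are used and no other ratio is given; alpha 0.05 (section VI), taken as two-sided. Let R be the set of (a, b) positive counts with Fisher p < 0.05. Then

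power = Σ over (a, b) in R of Bin(a; 25, p_C) × Bin(b; 25, p_T).

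- 70.5% v 29.5% (difference 0.41): 80.5%.
- 70% v 30%: 78.2%.

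The stated figure is reproduced.

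**5. False positives with no true effect.** The same sum is used, with common true positive rate p. The rates of 30-70%, the one switched call and the 5-point drift are assumptions, since the documents give no figure. Switching one call replaces (a, b) by (a+1, b−1) before testing, stopping at 25 and 0. Drift uses p_C = p + 0.05 and p_T = p − 0.05.

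| Scenario | p = 30% or 70% | p = 50% | Hypothesised direction only |
|---|---|---|---|
| Masked calls, one fixed readout | 2.3% | 3.3% | 1.1-1.6% |
| One call switched per arm | 5.3% | 6.3% | 5.1-5.9% |
| 5-point drift per arm | 6.6% | 7.9% | 6.5-7.7% |

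The drift result depends on the assumed size. At p = 50%, 52.5% v 47.5% gives 4.4% and 60% v 40% gives 23.7%.

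**6. Better of two assays chosen after seeing arm.** Simulation, 400,000 trials, latent correlation between assays 0 to 0.8, two-sided: about 4.1-4.5% at a rate of 30% or 70%, and 5.8-6.5% at 50%.

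**The case against.** **No leak is shown.** Assignments go from the Network office to the site coordinator, tamoxifen levels are measured in a separate shared resource, and no text says that arm travels with tissue. This stands in part. A reader might infer that the laboratory knows arm and that the result will be biased; the documents do not support that. They do give the PI role duties that carry arm information, and they state no barrier.

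**Assay choice matters little.** This largely stands. Fisher's test is conservative at 25 per arm, so choosing the better of two assays stays within 5% at rates of 30% or 70%. If both assays were tested and reported separately, the inflation would follow from the declared policy of no multiplicity correction.

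**The cut-off is not really free.** A reader might infer that choosing a cut-off on a graded signal could push the error to 10.5-13.4%. The plan does not support that for tumors. Section V ties quantitative ChIP to cultured cells, and the Background describes tumor ChIP qualitatively, close to a present/absent reading. An all-or-none signal leaves no cut-off to choose. Nor does any section make the two promoters separate trial endpoints.

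**It is a pilot.** Section VI calls the study investigational and expects a larger confirmatory trial. That limits the cost of an error and keeps this point minor, but the protection is nearly free.

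**Conclusion.** The point holds as a gap in protection. For the Aim 1 primary call, the supplied text states no masking to arm and no rule for turning ChIP and PLA into one positive or negative result. Unmasked reading is the larger concern: one switched call per arm roughly doubles the two-sided false-positive rate, from 2.3-3.3% to 5.3-6.3%, and a 5-point drift takes it to 6.6-7.9%. Free choice between two assays is modest, at about 4.1-6.5%. These are illustrations that rest on 25 per arm, a two-sided test and assumed error sizes; they do not estimate what will happen. It would be wrong to conclude that bias is demonstrated, or that power or sample size is at fault. Some pages were removed from the supplied text, so the finding covers only what remains. This is a cheap improvement, not a flaw that invalidates the design.

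**What to change.** Keep Fisher's test and the sample size. Add two items to sections V and VI:

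(a) Specimens for ChIP and PLA are sent under a study code held by the RPCI Network office. Operators and readers do not know arm or tamoxifen levels until all calls are locked.

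(b) Before unmasking, the rule for a positive patient is fixed. It may be one deciding assay or a written ChIP/PLA combination rule; a single assay is not required. The rule covers patients with only one assay result, saying whether they count or are replaced. Positivity is set against each assay's own negative controls: IgG and a non-specific site for ChIP, and a stated control for PLA.

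The cost is a few lines of text and one coding step at each site. The Network office already issues assignments to the University of Chicago (section VI, Randomization; Appendix 2, item 3) and could hold the code. With masked calls on one fixed readout, power stays at 80.5% for a 0.41 difference. If a combination rule is chosen, the 70% and 30% planning rates should be read as rates for the combined call.

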Standard surgical therapy will be offered to the patient based on the size, location of their tumor or presence of multiple tumors. After the completion of the surgical resection, two core biopsies of the surrounding normal breast tissue will be taken. One will be used to evaluate for tamoxifen and tamoxifen metabolite levels as well as estradiol and estrone levels in the breast tissue. The second will be stored for future pharmacogenomic studies.

Sequential compression devices (SCD's) will be used as part of standard of care for all women undergoing general anesthesia. Even though there is no data to suggest that a short intervention with tamoxifen will increase the risk of thrombosis, only women who get the tamoxifen arm will receive 5000u of subcutaneous heparin in the pre-operative holding area in addition to the use of SCD's for added prophylaxis.

Patients will undergo adjuvant therapy according to the findings of their surgical pathology. If the patient undergoes Oncotype testing as part of their standard of care, we will collect that information as part of our clinical data for analysis.

ENROLLMENT: Patients would be enrolled in this study at both the University of Chicago and the multidisciplinary breast clinic at RPCI. We plan to accrue 50 patients to this study over 9-year study duration. Anticipated rate of accrual would be 2-3 patients a month.

Tamoxifen is commercially available as a 20 mg tablet. The appropriate grant supporting the study will pay for the tamoxifen and will be provided free-of-charge to patients enrolled in this study.

V. REQUIRED STUDIES

Collaborating institutional staff pathologist will supervise all pathology examinations.

Estrogen Receptor, Progesterone Receptor And Her2 Expression Status:

Biopsy specimens: Estrogen and progesterone receptors are critical for inclusion in this protocol and should either be available as a part of routine analysis or will be done as a part of screening for this study in patients otherwise eligible for the study. Enrollment in the study will be predicated on the presence of ER based on an Allred score of 3 or above. The results of the p53 status will not be used for eligibility and will be determined at the end of study. HER2 expression status is not required prior to accrual.

Genotyping:

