Protein expression measured by IHC gives an ordinal variable (0, 1+, 2+, 3+). For each protein, the four-week intensity change ("post – pre" will be between -3 and 3) will be compared between treatment and control groups with the Wilcoxon-Mann-Whitney test. In the control group we expect little change because no treatment has been given between samples. For power calculations we assume 80% of patients in control will have no change and 10% will increase and decrease. As a hypothesis, we estimate half of patients in the treatment group will have no change and the rest will increase one (e.g. from 1+ to 2+) or two categories (e.g. from 1+ to 3+). From simulation we estimate the power to correctly reject the null hypothesis when this alternative is true is about 90%.

It is possible the response variables in Aims 1 and 2 are correlated with clinical factors such as patient age, smoking status, and position in menstrual cycle. Additional exploratory comparisons of response between treatment and control groups will be made after adjustment for clinical factors with linear or logistic regression as appropriate. These secondary analyses may have greater ability to detect a treatment difference by controlling variability unrelated to treatment. PK/PD data modeling was described previously. Pharmacogenomic data will be explored with the general linear model $Y = a + bG + e$, where genotype G is quantified 0, 1, 2 for aa , Aa , AA , respectively; for quantitative response Y , normal linear regression is used; for binary response, logistic regression is used.

Randomization:

Patients will be allocated to treatment or control by block randomization (block size=4). The randomization assignment list will be maintained at RPCI. The nurse/coordinator from University of Chicago will notify the RPCI Network office for a randomization assignment by sending the completed patient registration form to [contact]. The Network Monitor or designee will randomize the patient and send the randomization assignment to the nurse/coordinator at University of Chicago.

Management of Patients After Completion of Tamoxifen Treatment:

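### Fisher's exact test for the Aim 1 primary comparison is valid but needlessly conservative; Boschloo's exact test would give a free, modest and variable gain in power

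*Combined protocol and SAP*

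**What the plan says.** Section VI (Statistical Considerations) defines the Aim 1 primary endpoint as a binary result, ER alpha-p53 interaction positive or negative, in two independent groups. The planned test is given as "The proportions of patients with positive ChIP assay/PLA will be compared with Fisher's Exact Test". The power claim attached to this test reads "which has 80% power to detect a difference of about 0.41 between the two group", and the example offered is "a difference of 70% in the control group vs. 30% in the TAM group". On error control the section says "no correction for multiple testing will be made" and "p-values less than $\alpha=0.05$ will be deemed statistically significant".

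The number of patients is given elsewhere. Section IV, under Enrollment, says "We plan to accrue 50 patients to this study over 9-year study duration". The Randomization paragraph of Section VI says "Patients will be allocated to treatment or control by block randomization (block size=4"; it does not state the ratio. The end of the eligibility criteria defines as unevaluable those without enough tissue or "who come off early on tamoxifen, and will be replaced on study". The sidedness of the test and the sample size behind the power sentence are not written beside it. The only other analysis planned for this endpoint is an exploratory adjusted regression.

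**The concern.** Fisher's test conditions on both margins of the 2x2 table. This design fixes the arm sizes but not the total number of positive tumours. With about 25 per arm the conditional distribution is coarse, so the p-value often cannot fall just under 0.05 and the true error rate stays well below 5%. The unused error is power forgone.

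Boschloo's test uses the Fisher p-value as its ordering statistic and raises the cutoff as far as the maximum error over the unknown common proportion allows. It controls the error exactly and its rejection region contains Fisher's. At stake is how often the pilot's main comparison detects a real disruption of the interaction. The plan has little slack, because its own 70% v 30% example comes out slightly below 80%.

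**Working it through.** **Inputs.** Total 50 patients (Section IV). Two arms in blocks of four (Section VI), taken as 1:1, so 25 per arm. Alpha 0.05 (Section VI), taken as two-sided. Rates 0.70 v 0.30, and a difference of about 0.41 (Section VI), centred here on 50% as 0.705 v 0.295.

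**Formulas.** For a rejection region R of tables (x, y):
- Power = sum over R of Bin(x; n1, p1) × Bin(y; n2, p2).
- Size = maximum over a common p (0.001 grid) of the same sum with p1 = p2 = p.
- Fisher region: two-sided Fisher p ≤ 0.05.
- Boschloo region: all tables with Fisher p ≤ c, where c is the largest cutoff that keeps size ≤ 0.05. At 25/25 the one-sided cutoff is 0.0396, so c = 2 × 0.0396 = 0.0792, against Fisher's 0.05.

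**Step 1: reproduce the plan's figure.** Two-sided Fisher at 25/25 gives 80.5% for 0.705 v 0.295 and 78.2% for 0.70 v 0.30. This matches the stated 80% for a difference of about 0.41. The alternatives fit less well for 0.705 v 0.295: one-sided Fisher at 0.05 gives 87.6%, and the uncorrected pooled normal formula gives 84.8%. At 20 per arm two-sided Fisher gives 62.6%. The power sentence therefore rests on two-sided Fisher with 25 per arm.

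**Step 2: true type I error at 25/25.** The maximum is 3.3% for Fisher and 4.6% for Boschloo.

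**Step 3: power at 25/25.**

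| True rates | Fisher | Boschloo | Gain (points) |
|---|---|---|---|
| 70% v 30% | 78.2% | 79.3% | 1.1 |
| 70.5% v 29.5% | 80.5% | 81.5% | 1.0 |
| 80% v 40%, or 60% v 20% | 78.8% | 83.3% | 4.5 |
| 90% v 50% | 83.3% | 89.5% | 6.3 |

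Gains are taken from unrounded powers. Over all pairs that differ by 0.40, the smallest gain is 1.1 points, at 70/30, and the largest is 6.7, at 87/47.

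**Step 4: other arm sizes, 70% v 30%.**

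| Arms | Fisher | Boschloo | Gain (points) | Fisher maximum size |
|---|---|---|---|---|
| 24/26 | 79.0% | 81.9% | 2.9 | 3.7% |
| 24/25 | 81.0% | 81.1% | under 0.1 | 4.4% |
| 24/24 | 75.0% | 79.7% | 4.7 | 2.9% |
| 23/23 | 71.3% | 78.6% | 7.2 | 2.6% |
| 22/22 | 67.3% | 77.8% | 10.6 | 2.4% |
| 21/21 | 62.9% | 74.4% | 11.5 | 2.3% |
| 20/20 | 59.9% | 70.5% | 10.6 | 2.5% |
| 23/22 | 74.7% | 75.7% | 1.0 | 3.7% |
| 22/21 | 70.9% | 72.8% | 1.9 | 3.6% |
| 21/20 | 66.8% | 70.2% | 3.4 | 3.5% |

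The gain is never negative, but it is erratic. It is large for small equal arms and mostly disappears when the arms differ by one patient.

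**The case against.** The strongest defence is that nothing here is wrong. Fisher's test is conventional, valid and pre-specified, and the 80% was computed for it, so its conservatism is already in the stated power. On the only pair of rates that the plan names, the gain at the planned size is about 1 point. The study is a pilot, makes no multiplicity correction and expects a larger trial to follow. All of this stands, and it limits the point to efficiency.

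A reader might infer that the plan gives away about 10 points of power. The documents do not support that. Such a gain needs equal evaluable arms of about 20 to 22, and no such size is stated for Aim 1. There are two indirect routes to it:
- The Aim 2 effect size of 0.91 SD has 80.1% power at 20 per arm and 88.3% at 25. That implies a different sample size for Aim 2, and 20 per arm contradicts the Aim 1 power sentence.
- If the analysis were limited to p53 wild-type tumours, and the 19% mutant share in the Background's retrospective series applied, 25 × 0.81 = about 20 per arm would remain. The plan does not say that the Aim 1 test is restricted in this way.

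The replacement rule also works against shrinkage from missing tissue or early stopping of tamoxifen. At 20 per arm Boschloo's test still reaches only 70.5%, so it is no remedy for a shortfall in numbers.

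One part of the defence is weaker than it looks. At 25/25 the 70/30 pair is where the gain is smallest, and the plan offers it only as an example. Nor are final arms of exactly 25/25 assured, since 50 is not a multiple of the block size of four.

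**Conclusion.** The point holds as a free improvement, modest and variable in size. At 25/25 Fisher's test has a maximum true error of 3.3%, and replacing it with Boschloo's gains between 1.1 and 6.7 points for differences of 0.40, with 1.1 at the plan's own 70% v 30%. Close to that size the gain at 70/30 ranges from almost nil (24/25) to 2.9 points (24/26).

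It would be wrong to conclude that the stated power is incorrect, that Fisher's test is an error, or that a 10-point loss is built into the plan. The results rest on a two-sided test at 0.05, 1:1 allocation without stratification, and 50 evaluable patients. The first two are inferred, because the plan does not state them.

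**What to change.** Before any unblinded outcome data are seen, make three changes in Section VI:

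1. In the Aim 1 sentence, name Boschloo's unconditional exact test (two-sided, 0.05) in place of Fisher's.
2. Report with it a matching exact unconditional confidence interval for the difference in proportions.
3. Restate the power sentence for that test at 25 per arm: about 79% for 70% v 30%, and about 81.5% for a difference of 0.41 centred on 50%. Write the sample size, sidedness and allocation ratio beside it.

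The cost is a few lines of text. The test is in standard software, no patients are added, and the type I error stays at or below 5%. The one condition is timing: a change of primary test after results are visible would cost more in credibility than it gains in power.
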